**Table 5-1: Schedule of Analyses of Primary Endpoint in all Randomized Population**

	Interim DFS Analysis	Final DFS Analysis
Population	All Randomized Subjects	
Conditions	When 348 Events of DFS are observed in all Randomized Subjects	When 410 Events of DFS are observed in all Randomized Subjects
Expected Timing	45 months	60 months (43 months of accrual + 17 months of follow-up)
Nominal Significance Level/Power	0.01349149	0.02108499 / 87%
Lower Boundary for Statistical Significance	Observed hazard ratio of 0.76	Observed hazard ratio of 0.79

**Table 5-2: Schedule of Analyses of Primary Endpoint in Subjects with PD-L1 Expression  $\geq 1\%$**

	Interim DFS Analysis	Final DFS Analysis
Population	Subjects with PD-L1 Expression <math>\geq 1\%</math>	
Conditions	When 137 events of DFS are observed in subjects with PD-L1 expression $\geq 1\%$	When 162 events of DFS are observed in subjects with PD-L1 expression $\geq 1\%$
Expected Timing	45 months	60 months (43 months of accrual + 17 months of follow-up)
Nominal Significance Level/Power	0.01349149	0.02108499 / 80%
Lower Boundary for Statistical Significance	Observed hazard ratio of 0.65	Observed hazard ratio of 0.69

Key secondary endpoint of OS will be formally compared (in subjects with PD-L1 expression  $\geq 1\%$  and all randomized subjects) using a hierarchical procedure in each population.

### 5.1 Key OS secondary Endpoint Analyses

The secondary endpoint of OS will be formally compared (in subjects with PD-L1 expression  $\geq 1\%$  and all randomized subjects) using a hierarchical procedure in each population as discussed in Glimm et al. with overall alpha of 2.5% (two-sided) using Lan-DeMets alpha spending function with the O'Brien-Fleming type of boundary in East v6 for each endpoint.

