8.4.2.2 Secondary Endpoint Methods

The analyses for secondary endpoints of NUTRFS, DSS and OS will be performed in all randomized subjects as well as in subjects with PD-L1 expression level $\geq 1\%$.

The key secondary endpoint of OS distribution will be compared between treatment groups using a two-sided stratified log-rank test at the overall significance level of 2.5% (two-sided) each. These comparisons will be tested using hierarchical procedure in each population.

The OS HR and corresponding two-sided $100 \times (1 - \text{adjusted } \alpha)\%$ CIs will be estimated in a Cox proportional hazards model using treatment as a single covariate, stratified by PD-L1 status (only in the all randomized population comparison), prior neo-adjuvant cisplatin chemotherapy, positive lymph node status.

The NUTRFS HR and corresponding two-sided 95% CIs will be estimated in a Cox proportional hazards model using treatment as a single covariate, stratified by PD-L1 status (only in the all randomized population comparison), prior neo-adjuvant cisplatin chemotherapy, positive lymph node status.

NUTRFS and OS distribution curves will be estimated using Kaplan-Meier methodology by treatment arm. Median values and the corresponding two-sided 95% CIs using the log-log transformation will also be computed. NUTRFS and OS rates at 6 months, 1 year and 2 years (and yearly after depending on the follow-up) and the corresponding two-sided 95% CIs using the log-log transformation will be computed.

Cumulative incidence of DSS⁵¹ will be also estimated.

No formal comparison will be done for NUTRFS and DSS secondary endpoints.

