## **5 SAMPLE SIZE AND POWER**

The sample size for this study is based on a comparison of the DFS distribution between subjects randomized to receive nivolumab and subjects randomized to receive placebo. There will be two co-primary comparisons: in subjects with PD-L1 expression  $\geq 1\%$  and in all randomized subjects with an alpha allocation of 2.5% (two-sided) each.

The prevalence of subjects with PD-L1 expression  $\geq 1\%$  is expected to be around 42%. In time-to-events trials, the number of events and power may typically be calculated assuming an exponential distribution in each treatment arm. However for DFS, a meaningful number of long-term disease-free survivors may be observed. As a consequence, the DFS curves may not follow an exponential decay and a flattening of the curves may be observed toward the end of the tail. Consequently, an exponential cure rate distribution was used to calculate the sample size.

The exponential cure rate distribution can be described with following formula:

$$S(t) = p + (1 - p) * \{e^{-\alpha t}\},$$

where  $p$  is the cure rate and  $\alpha$  is the parameter of the exponential distribution for the non-cured population.

Based on historical data, median DFS distribution in the control arm is assumed to be 12 months with a 5 year DFS rate of 32% used as the cure rate (i.e.,  $p=0.32$  and  $\alpha=0.11$ ). It is also assumed that DFS distribution in control arm does not depend on the PD-L1 expression level. Cure rates in subjects with PD-L1 expression  $\geq 1\%$  and in the all randomized population for the experimental arm are targeted to be 54% and 47% respectively while non cured population is assumed to follow same distribution as in the control arm. It is assumed that the effect of nivolumab vs. placebo will be delayed. A study of nivolumab vs. ipilimumab in metastatic melanoma (CheckMate 238) suggested a 3-month delayed effect for nivolumab, therefore the model used for the experimental arm also assumes a 3-month delayed effect in subjects with PD-L1 expression  $\geq 1\%$  and in the all randomized population for the experimental arm.

Approximately 700 subjects will be randomized in 1:1 ratio to nivolumab arm and control arm respectively.

- Approximately 410 DFS events in all randomized subjects will provide around 87% power to detect an average HR of 0.72 with an overall type I error of 2.5% (two-sided)

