- Approximately 162 DFS events in subjects with PD-L1 expression  $\geq 1\%$  (~294 subjects) will provide around 80% power to detect an average HR of 0.61 with an overall type I error of 2.5% (two-sided).

The target average hazard ratios were obtained via simulation using above modeling.

It is expected that the required number of events in each population will be reached when all subjects will have at least a minimum of 17 months of follow-up.

An interim DFS analysis (in all randomized subjects and in subjects with PD-L1 expression  $\geq 1\%$ ) will also be performed when 85% of DFS events in all randomized subjects (i.e., 348 DFS events) and in subjects with PD-L1 expression  $\geq 1\%$  (i.e., 137 DFS events) will be observed. The alpha level for DFS will be adjusted for the planned interim analysis using Lan-DeMets alpha spending function with the O'Brien-Fleming type of boundary in East v6.

Assuming an average accrual rate of 16 subjects per month, the accrual will take approximately 43 months. The total duration of the study from start of randomization to final analysis of DFS is expected to be 60 months (43 months of accrual + 17 months of follow-up).

DFS analyses in all randomized population and in subjects with PD-L1 expression  $\geq 1\%$  are projected to occur 45 months after start of the study for the interim analyses and 60 months (43 months of accrual + 17 months of follow-up) for the final analyses (Table 5-1 and Table 5-2).

It is expected that interim DFS analysis (defined as analysis timepoint T1) in each population will occur at the same time. However, because the DFS event rate pattern may be different between all randomized population and subjects with PD-L1 expression  $\geq 1\%$ , the interim DFS analysis of each population might also occur separately.

The final analysis of DFS in each population will be performed at the same time when 410 and 162 events of DFS are observed in all randomized subjects and in subjects with PD-L1 expression  $\geq 1\%$ , respectively (defined as analysis timepoint T2).

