**In subjects with PD-L1 expression  $\geq 1\%$**

[figure not shown]
Similar procedure (with 2 interim OS analyses) will applied for the secondary endpoint comparisons in subjects with PD-L1 expression  $\geq 1\%$  and is summarized in [Figure 5.1-2](#).

OS could be formally compared:

- 1) at the final analysis of DFS (defined as T2) that will occur after 162 DFS events have been observed or at approximately 91 OS events observed, if no final DFS analysis is needed.
- 2) after 125 OS events have been observed (defined as T3).
- 3) after 166 OS events have been observed (defined as T4).

Approximately 166 OS events in subjects with PD-L1 expression  $\geq 1\%$  will provide approximately 82% power to detect an HR of 0.61 with an overall type I error of 2.5% (two-sided). This corresponds to a median increase from 4.6 years to 7.5 years under exponential assumption. Two interim analyses are planned for OS in all randomized subjects at ~55% (i.e., 91 events) and at 75% (i.e., 125 events) information fractions.

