## **7.5.3 Interim/Final Analyses of Disease-Free Survival and Overall Survival**

In addition to the formal planned interim and final analyses of DFS and OS, the Data Monitoring Committee (DMC) will have access to periodic un-blinded interim reports of efficacy and safety to allow a risk/benefit assessment. Details are included in the DMC charter.

The DMC will review the safety and efficacy data from the informal interim analyses and will determine if the study should continue with or without changes or if accrual should be stopped. Subject enrollment will continue while waiting for the DMC's decisions.

The chair of the DMC and the sponsor can call an unscheduled review of the safety data.

At the time of the formal interim analysis for superiority of DFS, the DMC may recommend continuing or stopping the trial.

- If the trial continues beyond the formal interim analysis, the nominal critical point for the final DFS analysis will be determined using the recalculated information fraction at the time of the interim analysis, as described above. The final DFS hazard ratio and corresponding confidence interval will be reported whereby the confidence interval will be adjusted accordingly (i.e. using the recalculated nominal  $\alpha$  level at the final analysis).

- If the trial is stopped for superiority of DFS at the interim, the p-value from the interim stratified log-rank test will be considered the final primary analysis result.  
If allowed per hierarchical testing procedure, at the time of the formal interim analyses for superiority of OS, the DMC may recommend continuing or stopping the trial (see [Section 5.1](#)).
- If the trial continues beyond the two formal interim analysis, the nominal critical point for the final OS analysis will be determined using the recalculated information fraction at the time of each interim analyses, as described above. The final OS hazard ratio and corresponding confidence interval will be reported whereby the confidence interval will be adjusted accordingly (i.e. using the recalculated nominal  $\alpha$  level at the final analysis).
- If the trial is stopped for superiority of OS at one of the interim analyses, the p-value from the interim stratified log-rank test will be considered the final primary analysis result.

The same above procedure applies independently in each co-primary population.

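### A free but optional gain: the valid 2.5%/2.5% split never passes a finished population's alpha to OS in the other population

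*SAP*

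**What the plan says.** SAP 5 sets the two DFS comparisons, in PD-L1 ≥1% and "in all randomized subjects with an alpha allocation of 2.5% (two-sided) each". SAP 2.1 and Protocol 3.1 explain that the even weighting is deliberate. OS follows DFS: Protocol 8.4.2.2 says "These comparisons will be tested using hierarchical procedure in each population", and SAP 5.1 tests OS "with overall alpha of 2.5% (two-sided) using Lan-DeMets alpha spending function". For PD-L1 ≥1%, SAP 5.1 adds: "Similar procedure (with 2 interim OS analyses) will applied for the secondary endpoint comparisons". SAP 7.5.3 closes with "The same above procedure applies independently in each co-primary population". SAP 7.5 gives an experiment-wise error of two-sided 0.05 and ties the confidence level to the nominal test level.

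Every boundary in SAP Tables 5-1, 5-2, 5-1.1 and 5-1.2 is computed at 2.5%. No readable text or table moves alpha between populations. The two hierarchy figures could not be read in the text reviewed; each is captioned for one population only.

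**The concern.** When DFS and OS have both been rejected in one population, that population has no hypothesis left to test, and its 2.5% does nothing further. Under a Bonferroni split, that amount can be handed to a hypothesis still open in the other population without exceeding 5% overall. The plan therefore gives up some power for the second OS claim without gaining any error control in return.

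At stake is only whether OS can be claimed in both populations rather than one. The first OS claim, the DFS results and the validity of the trial are not affected.

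**Working it through.** **1. Reproduce the plan's boundaries.** The spending function is Lan-DeMets O'Brien-Fleming: for two-sided level α, the one-sided amount spent by information fraction t is 2{1 − Φ(z₁₋α/₄/√t)}. The limiting hazard ratio at d events under 1:1 allocation is HR = exp(−2z/√d).

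- All randomized OS, fractions 0.57/0.75/1, α = 2.5%: nominal 0.001877/0.007260/0.022476, as in Table 5-1.1.
- PD-L1 ≥1% OS, fractions 0.55/0.75/1, α = 2.5%: nominal 0.001515/0.007368/0.022494, as in Table 5-1.2.
- DFS, fractions 0.85/1: 0.01349149/0.02108499, as in Tables 5-1 and 5-2.
- OS power: 88.0% with 404 events and HR 0.71 (stated 87%); 82.1% with 166 events and HR 0.61 (stated 82%).

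The SAP rounds its HR limits down (for example 0.7968 is printed as 0.79). This is necessary, because Protocol 8.5 describes them as values at or below which the result is significant.

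**2. Boundaries at 5% on the same fractions.**

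| OS population | Look (events) | z at 2.5% | z at 5% | Nominal at 5% | HR = exp(−2z/√d) | Rounded down |
|---|---|---|---|---|---|---|
| All randomized | 230 | 3.109 | 2.749 | 0.00598 | 0.6959 | 0.69 |
| | 303 | 2.685 | 2.377 | 0.01747 | 0.7610 | 0.76 |
| | 404 | 2.282 | 2.016 | 0.04385 | 0.8183 | 0.81 |
| PD-L1 ≥1% | 91 | 3.172 | 2.806 | 0.00502 | 0.5553 | 0.55 |
| | 125 | 2.680 | 2.371 | 0.01774 | 0.6543 | 0.65 |
| | 166 | 2.282 | 2.015 | 0.04389 | 0.7314 | 0.73 |

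**3. Error control.** Suppose 2.5% passes only after DFS and OS are both rejected in the giving population, and only to OS in the receiving one.

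- *A true null in each population:* no transfer can occur before a false rejection has been made. Each family makes its first false rejection with probability at most 2.5%, so the total is at most 2.5% + 2.5% = 5%.
- *True nulls in one population only, including DFS:* its OS is reached only through a false DFS rejection, at 2.5%.
- *Only OS null in one population:* every 5% boundary lies inside the 2.5% boundary at the same look, so using 2.5% early and 5% later rejects no more often than 5% throughout.

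Simulation agrees: one-sided experiment-wise error was 2.18% to 2.49% against a limit of 2.5%, over four null configurations.

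**4. Size of the gain.** The inputs from the plan are DFS HRs of 0.72/0.61 at 410/162 events and OS HRs of 0.71/0.61 at 404/166 events. The PD-L1 group is nested in the whole, so the correlation between populations is √(166/404) = 0.64 for OS and √(162/410) = 0.63 for DFS. The DFS–OS correlation is in neither document and is assumed.

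Constant HR, 600,000 simulated trials per setting:

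- Under the plan, with correlation 0 to 0.7 and the DFS gate included, the PD-L1 ≥1% OS claim succeeds in 66.5–71.1% of trials, the all-randomized OS claim in 75.4–78.6%, and at least one of the two in 84.5–86.7%.
- Transfer usable at the same look, correlation 0 to 0.9: +2.6 to 3.4 points (PD-L1 ≥1%) and +1.3 to 1.8 (all randomized).
- Transfer usable only at a strictly later look: +1.4 to 1.6 and +0.6 to 0.7.

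Patient-level simulation under the plan's cure-rate model, in which "the model used for the experimental arm also assumes a 3-month delayed effect", 20,000 trials per setting:

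- OS looks coincide: +2.2 to 3.5 and +1.3 to 1.9.
- Third and fourth time points triggered separately by each population's own event count: +1.8 to 2.9 and +0.8 to 1.1.
- Transfer only at a strictly later look: +1.0 to 1.6 and +0.6 to 0.7.

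This simulation gave average DFS HRs of 0.72/0.60 (stated 0.72/0.61) and DFS power of 85%/80% (stated 87%/80%).

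In every setting the chance of at least one OS claim changed by 0.00. That follows by construction, since alpha moves only after one OS claim has been made.

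**The case against.** The strongest reply is that this is a preference. The split is deliberate and valid, and SAP 7.5.3 already says the populations are handled independently, so the rule is not ambiguous. The gain is a few points at most and goes to a second claim in an overlapping population. The DMC already sees periodic unblinded efficacy reports, and Revised Protocol 5 has only just added an OS look, so a further change to the testing strategy would need justification. The OS confidence level in one population would also come to depend on the result in the other. All of this stands. It makes the point optional; it does not remove the gain.

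A reader might also infer stronger points that the documents do not support:

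- *That alpha is miscontrolled.* It is not: 2.5% + 2.5% = 5%.
- *That the trial becomes more likely to show an OS benefit.* It does not; only the second claim gains.
- *That the gain is much larger.* It would be about +5 to 13 points (PD-L1 ≥1%) and +2.5 to 6 (all randomized) if alpha could reach OS without DFS being won in the receiving population, but that abandons the plan's hierarchy. It would be +8.7 to 9.4 and +5.7 to 6.2 if the whole trial stopped at the first OS win. SAP 7.5.3 says only that "the DMC may recommend continuing or stopping the trial", and applies the procedure independently by population.

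Nor can it be assumed that both populations are always analyzed together. SAP 5 allows that "the interim DFS analysis of each population might also occur separately", and the later OS looks are defined by each population's own event count. This is why the range extends down to the later-look figures.

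**Conclusion.** The point holds as an optional improvement, not an error. At the design hazard ratios, passing a finished population's 2.5% to OS in the other adds about 1 to 3.5 points to the PD-L1 ≥1% OS claim and about 0.6 to 1.9 to the all-randomized OS claim. It adds nothing to the chance of at least one OS claim, and experiment-wise error stays at two-sided 5%.

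The range rests on the assumed DFS–OS correlation, the timing of the looks and the reading of the 3-month delay (treated arm equal to control until month 3, then falling to its target cure rate). A separate check, with the DFS gates set to exactly 87%/80%, gave +1.5/+0.85 at a correlation of 0.95. It gave up to +2.0 for all randomized when OS power was set to exactly 87%.

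The gain also moves with the true effects (constant HR, transfer at the same look):

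| True HRs | PD-L1 ≥1% OS | All-randomized OS |
|---|---|---|
| Equal in both (DFS 0.72, OS 0.71) | +3.9 to 4.3 | +0.3 |
| 0.80 all, 0.61 PD-L1 ≥1% | +0.5 to 0.6 | +4.2 to 4.4 |
| Design DFS; OS 0.77 all, 0.70 PD-L1 ≥1% | +5.0 to 5.3 | +2.5 to 2.6 |
| 0.80 in both | +1.0 to 1.6 | +0.2 to 0.4 |

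**What to change.** If the sponsor wants the gain, add to Protocol 8.5 and SAP 5.1 and 7.5.3, before any formal efficacy unblinding:

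> If DFS and OS are both rejected in one population, its 2.5% is reallocated to OS in the other population. From that data cut-off onward, OS there, if its own DFS has been rejected, is tested at an overall two-sided 5% with Lan-DeMets O'Brien-Fleming boundaries at the actual information fractions. Completed DFS analyses and earlier OS looks are not re-tested.

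Add 5% columns to SAP Tables 5-1.1 and 5-1.2, on the tables' own information fractions and with HR limits rounded down as in the SAP:

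- All randomized: nominal 0.00598/0.01747/0.04385, HR 0.69/0.76/0.81.
- PD-L1 ≥1%: nominal 0.00502/0.01774/0.04389, HR 0.55/0.65/0.73.

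Set the OS confidence level to the test level actually used. At the final all-randomized look, for example, that is 1 − 0.022476 = 97.75% without the transfer and 1 − 0.04385 = 95.6% with it.

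The cost is a protocol and SAP revision, with OS boundaries and confidence levels that depend on the other population's result. No patients, events or looks are added, no planned rejection is lost and no DFS result changes. If the sponsor prefers the present rule, no new text is needed, since SAP 7.5.3 already states independence.

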#### In all randomized subjects

[figure not shown]
OS could be formally compared either

- 1) at the final analysis for DFS (T2) that will occur after 410 events of DFS are observed or at approximately 230 OS events observed, if no final DFS analysis is needed.
- 2) after 303 OS events have been observed (T3).
- 3) after 404 OS events have been observed (T4).

This testing procedure is also summarized in [Figure 5.1-1](#).

Approximately 404 OS events in all randomized subjects will provide approximately 87% power to detect an HR of 0.71 with an overall type I error of 2.5% (two-sided). This corresponds to a median increase from 4.6 years to 6.5 years under exponential assumption. Two interim analyses are planned for OS in all randomized subjects at  $\sim 57\%$  (i.e., 230 events) and at 75% (i.e., 303 events) information fractions.

**Figure 5.1-1: Hierarchical Procedure with Group Sequential Testing in all Randomized Subjects**

**Table 5-1.1: Schedule of Analyses of OS, Key Secondary Endpoint, in all Randomized-Population**

	Interim OS Analysis #1	Interim OS Analysis #2	Final OS Analysis
Population	All Randomized Subjects		
Conditions	At final DFS analysis (ie approximately 230 OS events should be observed) OR when 230 OS events are observed, in case of no final DFS analysis	When 303 OS events are observed	When 404 OS events are observed
Expected Timing	60 months (T 2 )	75 months (T 3 )	105 months (T 4 )
Nominal Significance Level/Power	0.001877	0.007260	0.022476 / 87%
Lower Boundary for Statistical Significance	Observed hazard ratio of 0.66	Observed hazard ratio of 0.73	Observed hazard ratio of 0.79

**In subjects with PD-L1 expression  $\geq 1\%$**

[figure not shown]
Similar procedure (with 2 interim OS analyses) will applied for the secondary endpoint comparisons in subjects with PD-L1 expression  $\geq 1\%$  and is summarized in [Figure 5.1-2](#).

OS could be formally compared:

- 1) at the final analysis of DFS (defined as T2) that will occur after 162 DFS events have been observed or at approximately 91 OS events observed, if no final DFS analysis is needed.
- 2) after 125 OS events have been observed (defined as T3).
- 3) after 166 OS events have been observed (defined as T4).

Approximately 166 OS events in subjects with PD-L1 expression  $\geq 1\%$  will provide approximately 82% power to detect an HR of 0.61 with an overall type I error of 2.5% (two-sided). This corresponds to a median increase from 4.6 years to 7.5 years under exponential assumption. Two interim analyses are planned for OS in all randomized subjects at ~55% (i.e., 91 events) and at 75% (i.e., 125 events) information fractions.

**Figure 5.1-2: Hierarchical Procedure with Group Sequential Testing in the Subjects with PD-L1 Expression  $\geq 1\%$**

**Table 5-1.2: Schedule of Analyses of OS, Key Secondary Endpoint, in the subjects with PD-L1 expression  $\geq 1\%$**

	Interim OS analysis #1	Interim OS analysis #2	Final OS analysis
Population	Subjects with PD-L1 expression level $\geq 1\%$		
Conditions	At final DFS analysis (i.e. approximately 91 OS events should be observed) OR when 91 OS events are observed in subjects with PD-L1 expression level $\geq 1\%$ , in case of no final DFS analysis	When 125 OS events are observed in subjects with PD-L1 expression level $\geq 1\%$	When 166 OS events are observed in subjects with PD-L1 expression level $\geq 1\%$
Expected timing	60 months (T 2 )	75 months (T 3 )	105 months (T 4 )
Nominal significance level/Power	0.001515	0.007368	0.022494 / 82%
Lower boundary for statistical significance	Observed hazard ratio of 0.51	Observed hazard ratio of 0.61	Observed hazard ratio of 0.70

The interim and final DFS analysis are projected to occur around 45 and 60 months after the start of accrual (T1, T2), respectively followed by T3 (interim analysis of OS) around 75 months and T4 (final analysis of OS) around 105 months after the start of accrual.

